6.3.5 Correlative Studies

We will determine the prevalence of ESR1 mutations in plasma and metastatic biopsies of patients with metastatic breast cancer. We have an ongoing program for Sanger sequencing based detection of ESR1-mut in tumor specimens in the Division of Molecular Genomic Pathology of UPMC Magee-Womens Hospital. Detection of ESR1-mut in ctDNA will be performed at the UPMC Pathology laboratories. Patients in the trial will have blood assessed serially for the presence or absence of ESR1-mt to determine the mutational prevalence in a 2nd-3rd line ER+ MBC population with prior tamoxifen/AI exposure. We will also be able to follow the ctDNA levels over time in response to treatment. Patients with disease amenable to biopsy will be offered the option and encouraged to have a metastatic site biopsy performed prior to study treatment and again at the time of progression. The hypothesis is that circulating levels of ESR-mut will be detectable in 25% of patients in this setting (consistent with our pilot study) and will decrease in response to fulvestrant. Correlation of plasma results and tumor results will help to determine concordance between these two measurements as well as to assess for potential heterogeneity between plasma and a specific metastatic tumor site. For instance, while ESR1-mut have been previously identified in a number of metastatic sites including lymph node and liver metastases, there has not been identification of these mutations in bone specimens. Whether this is an effect of the tissue processing or whether there is truly biologic relevance to this remains to be seen. We may find that in plasma the detection of ESR1-mut may be much higher than the prevalence seen in metastatic biopsies for that reason (i.e. bone only ER+MBC). We will also perform ddPCR and NGS in ctDNA and tumor biopsies in conjunction with AstraZeneca scientists, as an additional exploratory objective for ESR and other co-existent mutations of interest. .

These tumor biopsies will be assessed for the most commonly described ESR1 mutations using Sanger sequencing of the three ESR1 exons, which will assess for 23 different ESR1 mutations (including the 6 most commonly described: S463P, L536Q, Y537S, Y537C, Y537N, and D538G)). These biopsies will also undergo next generation sequencing for other mutations that may be associated with ESR1-mut and could affect response to fulvestrant. This will be done using the MammoSeq assay developed at the UPMC Hillman Cancer Center, which includes genes commonly mutated in breast cancer, common actionable mutations in non-breast cancers, rare but actionable mutations such as ErbB2, as well as copy number amplifications and deletions. This will allow for determination of other mutations, such as PIK3CA, that are frequently encountered in ER+ MBC and could either be passenger mutations with the ESR1-mut or driver mutations that will provide greater influence over response to therapy. (see Table 3) Assessment of these mutations may also help to identify subsequent therapies for patients. As there is not any prospective data that currently uses molecularly targeted therapies towards other cancer genes (with exception of ER and HER-2) to guide therapies as a standard of care, we do not feel this should influence subsequent enrollment onto this trial of a standardly used agent. The hypothesis is that while 25% of ER+ MBC patients will have the most common ESR1-mut present in tumor specimens; there may be additional patients who will have other ESR1 alterations that will affect ESR1 activity and response to treatment. We will ask for archived tumor samples as well so that we can determine if the ESR1 mutation was acquired as a result of previous endocrine therapy or present at the time of diagnosis.

Metastatic biopsies obtained in the clinical trial will also undergo molecular analysis to determine the activity of mutant ESR1. Although tumors harboring ESR1 mutations appear to be acquired as a result of estrogen deprivation therapy (1-6), and patients with these particular tumors have a much worse overall survival (7), relatively little is known, mechanistically, about the role these mutants have in metastatic disease progression and tropism. We hypothesize that ESR1 mutants confer a selective advantage due not only to their intrinsic constitutive activity in the relative absence of estrogen, but also to their propensity to preferentially transactivate specific target genes, in response to microenvironment cues, that are required for tumor cell survival, colonization, and metastatic outgrowth. Thus, we anticipate that ER target gene expression profiles obtained from primary tumors and their matched ESR1-expressing metastatic counterparts will display distinct qualitative and/or quantitative differences. Furthermore, we hypothesize that a subset of genes from these derived differential gene signatures will be shared in metastases from the same distant sites among different patients harboring one of several ESR1 point mutations or gene fusions that also confer constitutive activity. This convergent mutant ER gene signature could then provide mechanistic insights into ESR1 metastatic dependencies and thus serve as a prognostic indicator of metastatic progression (and tropism) and as a predictive marker of therapeutic response to HD fulvestrant and next generation mutant ER-directed SERDs, SERMs, and allosteric antagonists. Most importantly, this approach offers the opportunity to correlate specific target gene expression with fulvestrant dose and clinical outcome and thereby elucidate the molecular basis for ESR1 conferred partial resistance to fulvestrant. Identifying these mutant ER-dependent essential genes could then define particular targeted combination strategies to address this resistance.

Our laboratories have developed and implemented methods for determining gene expression profiles from formalin-fixed paraffin embedded (FFPE) solid tumor biopsies that will be collected. We will use NanoString nCounter technology, which enables a highly multiplexed direct profiling of individual RNA molecules without amplification and is ideally suited for degraded RNA from small biopsy material (requiring only 100ng of RNA). We previously used nCounter to measure expression of genes (n=158) in the five major breast cancer molecular tests (PAM50, Oncotype Dx, BCI, MammaPrint and EndoPredict) and in the 78 cases of primary breast cancer measured we found the platform to be robust and highly reproducible. For this proposal, we have developed a wild type ER α target gene expression profile (n=208 genes) which is robustly increased or decreased by estrogen stimulation of ER α . Initially, to help validate this approach for discerning differences in ER-target gene expression profiles between wildtype and mutant ER at different estrogen and fulvestrant concentrations, we used CRISPR/cas9 targeted genome editing to generate isogenic pairs of T47D-derived cell lines expressing wildtype ER and its mutant (D538G)-expressing counterpart. Since it is quite possible that mutant ER can have specific target genes distinct from those of wild type ER (and therefore not be represented in our current probe kit), we will also conduct a gene expression microarray analysis using the isogenic cell line pair to identify potential mutant ER-specific target genes and accordingly expand our NanoString-based probe kit. The effect of estrogen and fulvestrant on gene expression profiles will be measured in vitro to produce a pharmacodynamic profile of receptor activity

TABLE 3. MammoSeq gene list:

ABL1	CDK4*	FGFR4*	KIT	NOTCH1
AKT1	CDKN1B	FOXA1	KRAS	NRAS
AKT3*	CDKN2A	GATA3	MAP2K4	PAK1*
ALK	CTNNB1	GRB7*	MAP3K1	PDGFRA
AR*	DNAH14	HIST2H2BE	MAP3K4	PIK3CA*
ARID1A	EGFR*	HLA-A	MDM2*	PIK3R1
ATM	ERBB2*	HRAS	MDM4*	PTCH1
AURKA*	ERBB3*	IDH1	MET*	PTEN
AURKB*	ERBB4	IGF1R*	MLL3	RB1
BRAF	ESR1*	INPP4B*	MTOR	RET
BRCA1	EZH2	INSR*	MYC*	RPTOR
BRCA2	FGF19**	JAK2*	NCOA3*	RUNX1
CCND1*	FGFR1*	JAK3*	NCOR1	SMO
CCNE1*	FGFR2*	JUN	NCOR2	STK11
CDH1	FGFR3	KDR	NF1	TP53

6.4 Safety

6.4.1 Definition of adverse events

An adverse event is the development of an undesirable medical condition or the deterioration of a pre-existing medical condition following or during exposure to a pharmaceutical product, whether or not considered causally related to the product. An undesirable medical condition can be symptoms (e.g., nausea, chest pain), signs (e.g., tachycardia, enlarged liver) or the abnormal results of an investigation (e.g., laboratory findings, electrocardiogram). In clinical studies, an AE can include an undesirable medical condition occurring at any time, including run-in or washout periods, even if no study treatment has been administered. The term AE is used to include both serious and non-serious AEs. Definition of AE will be in accordance to

the CTCAE version 4.03. All grades of AE's will be captured, greater than grade 1. AE's will start to be captured on day 1 of study drug administration.

6.4.2 Definitions of serious adverse event (SAE)

A serious adverse event is an AE occurring during any study phase (i.e., run-in, treatment, washout, follow-up), that fulfils one or more of the following criteria:

- Results in death
- Is immediately life-threatening
- Requires in-patient hospitalization or prolongation of existing hospitalization
- Results in persistent or significant disability/incapacity or substantial disruption of the ability to conduct normal life functions
- Results in a congenital abnormality or birth defect
- Is an important medical event that may jeopardize the subject or may require medical intervention to prevent one of the outcomes listed above.

6.4.3 Recording of Adverse Events

General: All adverse events will be captured on the appropriate study-specific case report forms (CRFs).

Serious Adverse Events: All serious adverse events, regardless of causality to study drug, will be reported to the Principal Investigator and/or the Study Coordinator at each institution, and also to the Coordinating Center.

All serious adverse events must be reported to the Coordinating Center within 1 business day after the investigator becomes aware of the event. Events should be reported using a MedWatch form (3500) as available on the FDA website (<http://www.fda.gov/Safety/MedWatch>). Follow-up information must also be reported within 1 business day of receipt of the information by the investigator.

The Coordinating Center will disseminate information regarding serious adverse events to the participating sites within 5 days of review of the information by the Protocol Chair (or her designee in the event of extended absence) only in the case that the event(s) is believed to be related (i.e., possibly, probably, or definitely) to the study medication.

The following variables will be collected for each AE:

- AE (verbatim)
- The date when the AE started and stopped
- CTCAE grade
- Whether the AE is serious or not
- Investigator causality rating against the Investigational Product (yes or no)
- Action taken with regard to investigational product
- AE caused subject's withdrawal from study (yes or no)
- Outcome.

In addition, the following variables will be collected for SAEs:

- Date AE met criteria for serious AE
- Date Investigator became aware of serious AE
- AE is serious due to
- Date of hospitalization
- Date of discharge
- Probable cause of death
- Date of death
- Autopsy performed
- Causality assessment in relation to Study procedure(s)
- Causality assessment in relation to Other medication
- Causality assessment in relation to Additional Study Drug
- Description of AE.

It is important to distinguish between serious and severe AEs. Severity is a measure of intensity whereas seriousness is defined. An AE of severe intensity need not necessarily be considered serious. For example, nausea that persists for several hours may be considered severe nausea, but not a SAE. On the other hand, a stroke that results in only a limited degree of disability may be considered a mild stroke but would be a SAE.

Adverse Events based on signs and symptoms

When collecting AEs, the recording of diagnoses is preferred (when possible) to recording a list of signs and symptoms. However, if a diagnosis is known and there are other signs or symptoms that are not generally part of the diagnosis, the diagnosis and each sign or symptom will be recorded separately.

Adverse Events based on examinations and tests

If deterioration in a laboratory value/vital sign is associated with clinical signs and symptoms, the sign or symptom will be reported as an AE and the associated laboratory result/vital sign will be considered as additional information. Wherever possible the reporting investigator uses the clinical, rather than the laboratory term (e.g., anemia versus low hemoglobin value). In the absence of clinical signs or symptoms, clinically relevant deteriorations in non-mandated parameters should be reported as AE(s).

Deterioration of a laboratory value, which is unequivocally due to disease progression, should not be reported as an AE/SAE.

Any new or aggravated clinically relevant abnormal medical finding at a physical examination as compared with the baseline assessment will be reported as an AE.

Disease progression

Disease progression can be considered as a worsening of a subject's condition attributable to the disease for which the investigational product is being studied. It may be an increase in the severity of the disease under study and/or increases in the symptoms of the disease. The development of new, or progression of disease, or death attributable to breast cancer should be considered as disease progression and not an AE. Events, which are unequivocally due to disease, should not be reported as an AE.

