5.2.1.1 Fulvestrant

Please refer to the package insert for complete prescribing and toxicity information.

1. Other Names
ICI-182, 780; Faslodex
2. Classification
Fulvestrant is an estrogen receptor down regulator. One of its main differences from tamoxifen and the other SERMs is its lack of agonistic activity. It represents a class of drug that binds, blocks and degrades the ER.
3. Mode of Action
Estrogen Receptor Antagonist.
4. Storage and Stability
Refrigerate, 2°-8°C (36°-46°F). To protect from light, store in the original carton until time of use.
5. Administration
Fulvestrant 500mg should be administered intramuscularly into the buttocks slowly (1-2 minutes per injection) as two 5mL injections, one in each buttock.
6. Supply
Fulvestrant is supplied as 50mg/ml injection in 5-mL syringes for intramuscular administration.
7. Incompatibilities
No known drug-drug interactions.
8. Adverse Effects
10% incidence reported:
 - a. Endocrine & metabolic: Hot flushes (7% to 13%)

- b. Hepatic: Alkaline phosphatase increased (>15%; grades 3/4: 1% to 2%),
transaminases increased (>15%; grades 3/4: 1% to 2%)
- c. Local: Injection site pain (12% to 14%)
- d. Neuromuscular & skeletal: Joint disorders (14% to 19%)

1% to 10% incidence reported:

- a. Cardiovascular: Ischemic disorder (1%)
- b. Central nervous system: Fatigue (8%), headache (8%)
- c. Gastrointestinal: Nausea (10%), anorexia (6%), vomiting (6%), constipation (5%),
weight gain (\leq 1%)
- d. Genitourinary: Urinary tract infection (2% to 4%)
- e. Neuromuscular & skeletal: Bone pain (9%), arthralgia (8%), back pain (8%),
extremity pain (7%), musculoskeletal pain (6%), weakness (6%)
- f. Respiratory: Cough (5%), dyspnea (4%)

\leq 1% incidence reported: (Limited to important or life-threatening; reported with 250 mg or 500 mg dose): Angioedema, hepatitis, hypersensitivity reactions, leukopenia, liver failure, osteoporosis, thrombosis, vaginal bleeding

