Missed doses of palbociclib (meaning doses that are missed for one day) should not be made up. For example, if a dose is entirely missed for one day, dose should be skipped and NOT retaken the next day; patients should resume regular dosing as prescribed the following day. If a dose is vomited at any time after taking palbociclib, a replacement dose should NOT be taken. Patients who inadvertently take 1 extra dose during a day must skip the next day's dose and notify his or her treating physician. If a patient takes more than two doses of palbociclib in a day, the patient should bring this to the attention of his or her treating physician.

Patients should be instructed to record daily administration of the study drugs in a drug or medication diary.

14. Supply

Palbociclib will be manufactured by Pfizer and provided by the study Sponsor as capsules containing 75 mg, 100 mg, or 125 mg equivalents of palbociclib free base. Palbociclib will be supplied to sites in High Density Polyethylene (HDPE) bottles containing 75 mg, 100 mg, or 125 mg capsules and are labeled for clinical use.

15. Incompatibilities

Please see the Palbociclib Package Insert for more details on the known medication interactions.

16. Adverse Effects

Likely (greater than or equal to 50% chance that this will happen):

• Neutropenia. A condition in which the number of white blood cells called neutrophils is abnormally low. This increases the risk of infection, which may be serious or life threatening. You will be monitored closely for this risk.

Frequent (between a 10 to 50% chance that this will happen):

• Fatigue. Participants experiencing fatigue while taking palbociclib should exercise caution when driving or operating machinery.

• Weakness

• Low number of red blood cells that can causes tiredness and shortness of breath. May require a blood transfusion. (Anemia)

• Diarrhea

• Nausea

• Low number of platelets, which may cause bleeding and bruising. Bleeding may be serious or life threatening and may require a blood transfusion.

• Decreased appetite

• Constipation

• Mouth blisters/sores

- Infection of the sinus or lung
- Vomiting
- Loss of touch or sensation of pins and needles or numbness on the skin

Occasional (Between a 1 to 10% chance that this will happen):

- Rash
- Bloating
- Temporary hair loss
- Swelling in extremities (hands and feet)
- Headache
- Nosebleed
- Muscle spasm
- Inflammation of the mucous membranes
- Fever
- Dry mouth

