9. STUDY MANAGEMENT

9.1 TABLE 4. Study timetable and end of study

Procedure	Screening ^a	Visit 1	Every 4 weeks	Every 8 weeks	Off Treatment	Follow Up
INFORMED CONSENT	X					
CLINICAL ASSESSMENTS						
Physical Exam	X	X	X ^b		X	X ^c
Medical History	X	X				X ^c
Vital Signs, Height, Weight	X	X ^d	X		X	(X)
ECOG Performance Status	X	X	X		X	
LABORATORY TESTS:						
Hematology (CBC with diff, platelets)	X	X ^e	X ^f		(X)	
Chemistries and liver function tests ^g	X	X ^e	X ^f		(X)	
PT, INR, PTT ^q	X					
Estradiol ^h	X					
Pregnancy Test ⁱ	X			X		
IMAGING:						
CT Chest/Abd/Pelvis ^j	X ^j			X	(X)	(X)
Brain MRI	X ^k				(X)	(X)
TREATMENT:						
Tamoxifen		X ^L				
Fulvestrant		X	X ^L			
Palbociclib		X ^P				

OTHER ASSESSMENTS:						
Concomitant Medication Review	X	X	X		X	
Symptom/Toxicity Assessment	X	X	X		X ^m	
Follow-up/Survival					X ⁿ	X ^c
CORRELATIVE STUDIES						
Blood collection for ESR1-mt analyzed by ct-DNA	X		X		X	
Archived tissue sample (from breast primary)	X					
Optional Solid Tumor Biopsy	X ^o				X ^o	

- a) Screening assessments are required within 28 days of initiation of treatment unless otherwise noted.
- b) Required ≤ 1 day prior to each specified treatment (exceptions may be made to extend this window, with approval by the Protocol Chair/designee).
- c) To continue until patient death
- d) Height at baseline only
- e) Required ≤ 14 days prior to first day of treatment; baseline labs may be used if within window.
- f) Required ≤ 1 day prior to each specified treatment (exceptions may be made to extend this window, with approval by the Protocol Chair/designee).
- g) Chemistries to include measurement of sodium, potassium, chloride, CO₂, BUN, creatinine, glucose, total bilirubin, calcium, total protein, albumin, AST, ALT, and alkaline phosphatase.
- h) Estradiol if required to determine post-menopausal status can be performed any time prior to Visit 1 treatment
- i) Serum Pregnancy test is required for women of childbearing potential only. Required ≤ 7 days prior to first treatment (i.e., day 1) unless otherwise noted. All outcomes of pregnancy should be reported to the PI and AstraZeneca.
- j) PET/CT is allowed and the choice between using a CT or PET with CT will belong to the treating physician. If a PET is chosen, the CT is mandatory and must be of diagnostic quality.
- k) Only if known CNS metastasis

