11.2 Calculation or derivation of safety variable(s)

All adverse events will be captured on the appropriate study-specific case report forms (CRFs) and will be calculated as a frequency of occurrence according to the CTCAE v4.03. The frequency of adverse events will be categorized in accordance to the grading system present in CTCAE v4.03, using the highest grade recorded for each AE for each patient. AE rates will be calculated from the tamoxifen plus palbociclib and fulvestrant plus palbociclib cohorts and compared using the mid-p correction to Fisher's exact test.

12 . STATISTICAL METHODS AND SAMPLE SIZE DETERMINATION

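### Section 6.4.3 gives no reporting rule for symptom-free deterioration on the scheduled blood tests and by implication conflicts with 6.4.1, so the adverse event table may under-count neutropenia and other laboratory toxicity

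*Combined protocol and SAP*

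**What the plan says.** Section 6.4.3, under its heading on examinations and tests, has three rules for laboratory changes.

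- With symptoms: "the sign or symptom will be reported as an AE and the associated laboratory result/vital sign will be considered as additional information".
- Without symptoms: "In the absence of clinical signs or symptoms, clinically relevant deteriorations in non-mandated parameters should be reported as AE(s").
- Explicit exclusion: "Deterioration of a laboratory value, which is unequivocally due to disease progression, should not be reported as an AE/SAE".

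Section 6.4.1 is broader. Its definition of an adverse event includes "abnormal results of an investigation (e.g., laboratory findings, electrocardiogram"), with no condition about symptoms and no split by whether the test is mandated. It applies CTCAE version 4.03 and captures events above grade 1.

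Table 4 in section 9.1 lists "Hematology (CBC with diff, platelets") and the chemistries and liver tests at screening, at visit 1 and every 4 weeks. Footnote g names AST, ALT, alkaline phosphatase and total bilirubin.

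Safety and toxicity is primary objective 4 (section 2.1). Under section 11.2, adverse events go onto the case report forms and "will be calculated as a frequency of occurrence according to the CTCAE v4.03", using each patient's worst grade per event, and rates are compared between arms. Section 12.1 tabulates adverse events by treatment group. Neither section plans a table built from the laboratory values.

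**The concern.** The word non-mandated has no function in 6.4.3 unless scheduled tests are to be treated differently. That would be reasonable if scheduled values were summarised elsewhere, but no such summary is planned. A coordinator who looks up how to handle a symptom-free low count finds this specific rule, and the rule does not cover the case.

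The gap falls on the toxicity the protocol most expects. Section 5.2.1.2 (Palbociclib) places neutropenia, alone, under "Likely (greater than or equal to 50% chance that this will happen"). Section 1.1 reports neutropenia and leukopenia among the most common grade 3 or 4 events in the confirmatory phase 3 trial of palbociclib plus letrozole. A scheduled count can show either one without any symptom. If some sites follow 6.4.1 and others follow 6.4.3, the reported rate depends partly on where patients were treated. Section 3.1 allows up to 4 sites and section 12.2 plans 20 patients per arm, so one site's habit can visibly move a rate.

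**Working it through.** The plan states no figure on this point, so there is none to reproduce. The check is a comparison of rules, followed by a calculation of scale.

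**1. How each rule treats a symptom-free grade 2 or higher neutropenia found on a scheduled count**

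| Place | Result |
|---|---|
| 6.4.1, definition and grade threshold | Adverse event; captured |
| 6.4.3, general rule | Goes on the case report form if it is an adverse event |
| 6.4.3, rule with symptoms | Does not apply |
| 6.4.3, rule without symptoms | Names non-mandated parameters; silent on this one |
| 6.4.3, progression exclusion | Does not apply unless progression is clearly the cause |
| 11.2 and 12.1 | Counted if it was reported |

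The documents do not define mandated. I take it to mean required by Table 4. On that meaning, the blood count and chemistry fall outside the one rule written for symptom-free changes.

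**2. Scale**

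Inputs:
- n = 20 per arm, 40 in total (section 12.2).
- p = 0.50, the lower bound for neutropenia (section 5.2.1.2, Palbociclib).
- s = symptom-free share. The documents do not give it; assumed 25% to 95%.

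Expected cases: 20 × 0.50 = 10 per arm, or 40 × 0.50 = 20 in total.

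If every site takes the restrictive reading, cases omitted = 20 × s and recorded rate = 0.50 × (1 − s).

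| s (assumed) | Omitted, of 20 cases | Recorded, of 40 patients | Recorded rate |
|---|---|---|---|
| 25% | 5 | 15 | 37.5% |
| 50% | 10 | 10 | 25% |
| 75% | 15 | 5 | 12.5% |
| 95% | 19 | 1 | 2.5% |

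If every site follows 6.4.1, no case above grade 1 is omitted.

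In a mixed situation, let f be the fraction of patients at sites using the restrictive reading. The recorded rate is then 0.50 × (1 − f × s). With f = 0.5 (assumption) and s = 50%, it is 0.50 × (1 − 0.25) = 37.5%. With f = 0.5 and s = 95%, it is 0.50 × (1 − 0.475) = 26.25%.

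The protocol does not say which grades its 50% covers. Because 6.4.1 captures events above grade 1, the true base for the table may be lower. The proportional loss, f × s, does not depend on that base.

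**The case against.** The strongest reply is that 6.4.3 excludes nothing here. It does not say that non-mandated parameters are the sole reportable ones, and its one explicit laboratory exclusion concerns progression. The general rule in the same section sends every adverse event to the case report form. Section 7.2 says the safety blood is drawn to monitor adverse events. Section 6.4.3 also asks for clinical terms in place of laboratory terms and uses anemia as its example. Anemia is found on the scheduled blood count, so the section itself expects some count findings to be adverse events.

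All of this stands. It defeats the stronger inference a reader might draw, that asymptomatic neutropenia and liver-enzyme rises are certain to disappear from the table. It does not remove the conflict. The anemia example governs which term to use, section 7.2 gives a purpose, and the general rule does not say which laboratory results qualify. The specific sentence still points away from 6.4.1.

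Three other stronger inferences also fail:

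- **Bias between arms.** Section 5.2.2 gives palbociclib in both arms, so under-recorded neutropenia need not favour either one.
- **A lost liver-enzyme contrast.** Section 5.2.1.1 lists "transaminases increased (>15%; grades 3/4: 1% to 2"%) for fulvestrant. The figure above 15% is not limited to grades above 1, and the tamoxifen list gives AST, a different measure. Nor are the listed differences between the endocrine drugs mainly laboratory ones: sections 3.2 and 5.2.1 include injection-site pain, vaginal discharge, fluid retention and hot flashes.
- **No laboratory results reach the coordinating center.** The per-cycle list in section 6.2 does not name them, but that section also requires source documentation as set out in the case report forms, which are not part of these documents.

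**Conclusion.** The concern holds as an unresolved conflict. Section 6.4.3 is silent on symptom-free deterioration in mandated parameters and by implication leaves it out, whereas 6.4.1 includes it above grade 1. Neutropenia, leukopenia and liver-enzyme rises may be recorded differently across sites, and no planned laboratory table would recover what is missed.

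The size is conditional. The 37.5% to 2.5% range for recorded neutropenia rests on the assumed symptom-free share, on the restrictive reading at every site, and on the 50% base applying above grade 1. With mixed practice the loss is smaller; under 6.4.1 it is nil. The expected consequence is understated toxicity rates.

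This should be fixed. It affects the data behind a primary objective and the main expected toxicity. It does not invalidate a 40-patient pilot.

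**What to change.** Reconcile 6.4.3 with 6.4.1 by replacing the sentence on symptom-free changes, for example: *When the patient has no related symptoms, any clinically relevant laboratory deterioration above grade 1 is reported as an adverse event and graded by CTCAE v4.03, whether or not the protocol mandates the test.* Keep the existing exclusion for deterioration that is clearly the result of progression. The convention for changes that come with symptoms can stay as it is.

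In section 11.2, add a table by arm of each patient's worst CTCAE grade, derived directly from the scheduled blood count and chemistry values. This makes the laboratory toxicity rates independent of how each site reads 6.4.3.

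The cost is one sentence, one derived table, more adverse event lines, and entry of results the sites already hold. No new samples are needed.
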